14.1.1.1 Measurable

Tumor lesions: Must be accurately measured in at least one dimension (longest diameter in the plane of measurement is to be recorded) with a minimum size of:

- 10mm by CT scan (CT scan slice thickness no greater than 5 mm).
- 10mm caliper measurement by clinical exam (lesions which cannot be accurately measured with calipers should be recorded as non-measurable).
- 20mm by chest X-ray.

Malignant lymph nodes: To be considered pathologically enlarged and measurable, a lymph node must be ≥ 15 mm in short axis when assessed by CT scan (CT scan slice thickness recommended to be no greater than 5 mm).

14.1.1.2 Non-measurable

All other lesions, including small lesions (longest diameter <10 mm or pathological lymph nodes with ≥ 10 to <15 mm short axis) as well as truly non-measurable lesions. Lesions considered truly non-measurable include: Leptomeningeal disease, ascites, pleural or pericardial effusion, inflammatory breast disease, lymphangitic involvement of skin or lung, abdominal masses/abdominal organomegaly identified by physical exam that is not measurable by reproducible imaging techniques.

14.1.1.2.1 Bone lesions

- B, PET and plain films are not adequate to measure bone lesions; they may be used to determine the presence or absence of a lesion.
- Lytic or lytic-blastic lesions with identifiable soft tissue component that can be measured by CT or MRI and meets size requirement can be considered measurable. Blastic bone lesions are non-measurable.

14.1.1.2.2 Cystic lesions

- Cystic lesions that meet the criteria for simple cysts are not measurable.
- Cystic lesions that are thought to be cystic metastatic disease can be considered measurable disease, however if non-cystic lesions are present in the same patient these are preferable to include as target lesions.

14.1.1.2.3 Lesions previously treated

- Lesions within radiotherapy ports or who have been subject to other loco-regional treatment are usually not considered to be measurable and will be allowed on this study only with approval of the sponsor.

14.1.2 Specification by methods of measurement

14.1.2.1 Measurement of lesions

All measurements should be taken and recorded in metric notation. The same method of assessment and the same technique should be used to characterize each identified and reported lesion at baseline and during follow-up.

14.1.2.1.1 Target lesions

All lesions up to a maximum of five lesions total (and a maximum of two lesions per organ) representative of all involved organs should be identified as target lesions. If the largest lesion does not lend itself to reproducible measurement, the next largest lesion which can be measured reproducibly should be selected.

Pathological lymph nodes which are measurable may be identified as target lesions if they have a short axis of $\geq 15\text{mm}$ by CT scan. Only the short axis of these nodes will contribute to the baseline sum. Nodal size is normally reported as two dimensions in the plane in which the image is obtained. The smaller of these measures is the short axis. All other pathological nodes (those with short axis $\geq 10\text{mm}$ but $< 15\text{ mm}$) should be considered non-target lesions. Nodes that have a short axis $< 10\text{mm}$ are considered non-pathological and should not be recorded or followed.

14.1.2.1.2 Non-target lesions

All other lesions (or sites of disease) should be identified as *non-target lesions* and should also be recorded at baseline. It is possible to record multiple non-target lesions involving the same organ as a single item on the case record form (e.g. “multiple enlarged pelvic lymph nodes” or “multiple liver metastases”). Measurements of these lesions are not required, but the presence or absence of each should be noted throughout follow-up.

14.1.2.2 Response criteria

14.1.2.2.1 Evaluation of target lesions

This section provides the definitions of the criteria used to determine overall tumor response for target lesions as shown below in [Table 14-1](#).

Table 14-1 Evaluation of target lesions

Response Criteria	Evaluation of target lesions
Complete Response (CR):	Disappearance of all target lesions. Any pathological lymph nodes (whether target or non-target) must have reduction in short axis to <10 mm. ¹
Partial Response (PR):	At least a 30% decrease in the sum of diameters of target lesions, taking as reference the baseline sum diameters.
Progressive Disease (PD):	At least a 20% increase in the sum of diameter of all measured target lesions, taking as reference the smallest sum of diameter of all target lesions recorded at or after baseline. In addition to the relative increase of 20%, the sum must also demonstrate an absolute increase of at least 5 mm (Note: the appearance of one or more new lesions is also considered progression)
Stable Disease (SD):	Neither sufficient shrinkage to qualify for PR nor sufficient increase to qualify for PD, taking as reference the smallest sum diameters while on study

Notes on the assessment of Lymph nodes: Lymph nodes identified as target lesions should always have the actual short axis measurement recorded (measured in the same anatomical plane as the baseline examination), even if the nodes regress to below 10mm on study. This means that when lymph nodes are included as target lesions, the ‘sum’ of lesions may not be zero even if complete response criteria are met, since a normal lymph node is defined as having a short axis of <10mm. In order to qualify for CR, each node must achieve a short axis <10mm. For PR, SD and PD, the actual short axis measurement of the nodes is to be included in the sum of target lesions.

14.1.2.2.2 Evaluation of non-target lesions

This section provides the definitions of the criteria used to determine the tumor response for the group of non-target lesions as shown below in [Table 14-2](#). While some non-target lesions may actually be measurable, they need not be measured and instead should be assessed only qualitatively at the time points specified in the protocol.

Table 14-2 Evaluation of non-target lesions

Response Criteria	Evaluation of target lesions
Complete Response (CR):	Disappearance of all non-target lesions and normalization of tumor marker level. All lymph nodes must be non-pathological in size (<10mm short axis)
Non-CR/Non-PD:	Persistence of one or more non-target lesion(s) and/or maintenance of tumor marker level above the normal limits.
Progressive Disease (PD):	Unequivocal progression of existing non-target lesions. (Note: the appearance of one or more new lesions is also considered progression).

[figure not shown]
14.1.2.2.3 New lesions

The appearance of a new lesion is always associated with Progressive Disease (PD) and has to be recorded appropriately in the eCRF.

- If a new lesion is **equivocal**, for example because of its small size, continued therapy and follow-up evaluation will clarify if it represents truly new disease. If repeat scans confirm there is definitely a new lesion, then progression should be declared using the date of the first observation of the lesion.
- If new disease is observed in a region which **was not scanned at baseline** or where the particular baseline scan is not available for some reason, then this should be considered as

a PD. The one exception to this is when there are no baseline scans at all available for a patient in which case the response should be UNK, as for any of this patient's assessment.

- A **lymph node is considered as a “new lesion”** and, therefore, indicative of progressive disease if the short axis increases in size to ≥ 10 mm for the first time in the study plus 5 mm absolute increase.
 - a. Negative FDG-PET at baseline, with a positive¹ FDG-PET at follow-up is a sign of PD based on a new lesion.
 - b. No FDG-PET at baseline and a positive FDG-PET at follow-up: If the positive FDG-PET at follow-up corresponds to a new site of disease confirmed by CT, this is PD. If the positive FDG-PET at follow-up is not confirmed as a new site of disease on CT, additional follow-up CT scans are needed to determine if there is truly progression occurring at that site (if so, the date of PD will be the date of the initial abnormal FDG-PET scan). If the positive FDG-PET at follow-up corresponds to a pre-existing site of disease on CT that is not progressing on the basis of the anatomic images, this is not PD.

14.2.1 Definitions and criteria for normalization

14.2.1.1 Definitions

14.2.1.1.1 Nodal vs extranodal lesion

A lesion is categorized based on the location as:

- **Nodal lesion**,
- **Extranodal lesion**, if it is located in organs other than lymph node or nodal mass, but including spleen and liver.

14.2.2 Measurability of Tumor Lesions at Baseline

All tumor lesions/lymph nodes will be categorized as measurable or non-measurable as follows:

14.2.2.1 Measurable Nodal and extranodal lesions

A lesion will be called **measurable** if it can be measured accurately in 2 perpendicular dimensions and:

- For nodal lesion, if the long axis is > 15 mm, regardless of the length of the short axis,
- For extranodal lesion, if the long and short axes are ≥ 10 mm.

Patients should have at least one measurable nodal lesion greater than 20 mm in the long axis.

In cases where the patient has no measurable nodal lesions greater than 20 mm in the long axis at Screening, then the patient must have at least one measurable extranodal lesion.

14.2.2.2 Classification of lymph nodes

Lymph nodes are classified according to their size and/or relationship to the disease:

- A lymph node meeting the measurability requirement above will constitute a **measurable nodal lesion**.
- A lymph node not meeting the measurability requirement but with long axis > 15 mm (e.g. short axis cannot be measured accurately) will constitute a **non-measurable nodal lesion**.
- A lymph node not meeting the measurability criteria but with a size of 11 mm to 15 mm in the long axis and > 10 mm in the short axis will be checked for relationship to disease:
 - If it is thought to be disease related, it will constitute a **non-measurable nodal lesion**.

- If it is not thought to be disease related, it will constitute an **abnormal lymph node** but not a lesion.
- All other lymph nodes will be considered normal and will not constitute nodal lesions.

14.2.2.3 Criteria for normalization of lesions

The normalization of lesions is defined as follow:

- A measurable nodal lesion must become ≤ 15 mm in long axis to be considered normalized.
- A non-measurable nodal lesion must decrease to ≤ 10 mm in the short axis and be ≤ 15 mm in long axis to be considered normalized.
- An extranodal lesion must disappear completely (assigned a size of 0 mm x 0 mm) to be considered normalized.

14.2.3 Specification by methods of measurement

14.2.3.1 Measurement of lesions

All radiological measurements should be taken in two perpendicular dimensions and recorded in metric notation, using a ruler or calipers.

14.2.3.1.1 PET

Visual assessment currently is considered adequate for determining whether a PET scan is positive, and use of the standardized uptake value is not necessary.¹ In brief, a positive scan is defined as focal or diffuse FDG uptake above background in a location incompatible with normal anatomy or physiology, without a specific standardized uptake value cutoff.¹ Other causes of false-positive scans should be ruled out. Exceptions include mild and diffusely increased FDG uptake at the site of moderate- or large-sized masses with an intensity that is lower than or equal to the mediastinal blood pool, hepatic or splenic nodules 1.5 cm with FDG uptake lower than the surrounding liver/spleen.

14.2.3.1.2 CT scan (or MRI)

For optimal evaluation of patients, the same methods of assessment and technique should be used to characterize each identified and reported lesion at Screening and during follow-up. Contrast-enhanced CT of chest, abdomen and pelvis should preferably be performed using a 5mm slice thickness with a contiguous reconstruction algorithm. CT/MRI scan slice thickness should not exceed 8 mm cuts using a contiguous reconstruction algorithm. If at Screening a patient is known to be allergic to CT contrast or develops allergy during the trial, the following change in imaging modality will be accepted for follow up: a non-contrast CT of chest (MRI not recommended due to respiratory artifacts) plus contrast-enhanced MRI of abdomen and pelvis.

A change in methodology can be defined as either a change in contrast use (e.g. keeping the same technique, like CT, but switching from with to without contrast use or vice-versa, regardless of the justification for the change) or a change in technique (e.g. from CT to MRI, or vice-versa), or a change in any other imaging modality. A change in methodology will

result by default in an “Unknown” overall radiological response assessment. However, another overall radiological response than the Novartis calculated “Unknown” response may be accepted from the investigator if a definitive overall radiological response can be justified to be based on the available information.

In order to calculate the sum of the product of the diameters (SPD) of all index lesions (or extranodal lesions), their size must be entered throughout the study.

Actual lesion measurements should be entered on the corresponding eCRFs. If, during the course of the study, either of the perpendicular diameters of a lesion cannot be reliably measured because of its small size, it is recommended to enter the minimum limit of detection as the diameter size (e.g. 5 mm for spiral CT). In other cases when, during the course of the study, the diameter cannot be reliably measured for reasons other than its size (i.e. borders of the lesion are confounded by neighboring anatomical structures), no measurement should be entered and the lesion cannot be evaluated.

If lesions become confluent over time, it is recommended to measure them as one lesion, report the overall diameters to one of the lesions and assign 0 mm x 0 mm to each of the other previously measured lesions. If a lesion splits during the study, each sub-lesion should be measured separately for all subsequent assessments and all sub-lesions contribute to the SPD.

14.2.3.1.3 Bone marrow assessment

Documentation of status of bone marrow involvement by lymphoma based on prior bone marrow biopsy or aspirate findings is required at Screening for all patients.

If no such documentation is available then a bone marrow biopsy or aspirate should be performed at Screening.

If bone marrow involvement is assessed by biopsy, the biopsy sample should have a goal of > 20 mm unilateral core. If the biopsy sample is indeterminate by morphology (immunohistochemistry), then flow cytometry may be performed on bone marrow aspirate to confirm the findings.

14.2.3.1.4 Physical examination and assessment of B-symptoms

Skin lesions, if the size is ≥ 20 mm in at least one diameter, must be histologically confirmed for lymphoma involvement (the investigational site must document the histological confirmation (yes or no) on the corresponding eCRF) and photographed including a ruler (color photography using digital camera). Tumor assessment will be performed and results will be recorded on the corresponding eCRF at Screening and at Day 1 of every cycle (± 4 days) after first dose of study drug.

B-symptoms are of importance in determining prognosis and should resolve completely in patients who have achieved complete response. B-symptoms in lymphoma patients are disease related clinical symptoms and are not caused by anticancer therapy (or drug toxicity).

B-symptoms are defined as follows:

- Significant unexplained fever ($\geq 38^{\circ}\text{C}$),
- Unexplained, recurrent drenching night sweats

- Unexplained loss of > 10% body weight within the previous 6 months, as assessed and reported (present vs. absent) by the Investigator.

14.2.4 Evaluation of Radiological Response

For the sake of simplicity, complete remission and complete response will both be referred to as complete response.

Definitions of Response for Lymphoma patients are listed in [Table 14-6](#). To evaluate disease response to treatment, all index and non-index lesions will be followed and assessed throughout the study. At each assessment, response is evaluated separately for the **index lesions** ([Table 14-9](#)) and **non-index lesions** ([Table 14-8](#)) identified at Screening, then a combined overall radiological response is determined ([Table 14-11](#)).

Table 14-6 Response Definition for Lymphoma

Response	Definition	Nodal Masses	Spleen. Liver	Bone Marrow
CR	Disappearance of all evidence of disease	a FDG-avid or PET positive prior to therapy; mass of any size permitted if PET negative b Variably FDG-avid or PET negative; regression to normal size on CT	Not palpable, nodules disappeared	Infiltrate cleared on repeat biopsy; if indeterminate by morphology, immunohistochemistry should be negative
PR	Regression of measurable disease and no new sites	≥ 50% decrease in SPD of up to 6 largest dominant masses; no increase in size of other nodes a FDG-avid or PET positive prior to therapy; one or more PET positive at previously involved site b Variably FDG-avid or PET negative; regression on CT	≥ 50% decrease in SPD of nodules (for single nodule in greatest transverse diameter); no increase in size of liver or spleen	Irrelevant if positive prior to therapy; cell type should be specified
SD	Failure to attain CR/PR or PD	a FDG-avid or PET positive prior to therapy; PET positive at prior sites of disease and no new sites on CT or PET b Variably FDG-avid or PET negative; no change in size of previous lesions on CT		
Relapsed disease or PD	Any new lesion or increase by ≥ 50% of previously involved sites from nadir	Appearance of a new lesion(s) > 1.5 cm in any axis, ≥50% increase in SPD of more than one node, or ≥ 50% increase in longest diameter of a previously identified node > 1 cm in short axis Lesions PET positive if FDG-avid lymphoma or PET positive prior to therapy	> 50% increase from nadir in the SPD of any previous lesions	New or recurrent involvement

14.2.4.1 Evaluation of Index Lesions (nodal and extranodal)

14.2.4.1.1 When index nodal lesions are not in complete response

The response for index lesions is evaluated by calculating the Sum of the Products of Diameters (SPD) of all index lesions (see [Table 14-7](#)), except when there is a Complete Response for index nodal lesions (i.e. complete normalization of all index nodal lesions) (see [Section 14.2.4.1.2](#)).

Table 14-7 Radiological status based on SPD calculation for all index lesions

Response Criteria ¹	Evaluation of index lesions
Complete Response (CR)	See Table 14-9 below (not based on SPD calculation for all index lesions)
Partial Response (PR)	At least 50% decrease from Screening in the SPD of all index lesions
Stable Disease (SD)	Failure to attain the criteria needed for CR or PR and failure to fulfill the criteria for PD
Progressive Disease (PD)	At least a 50% increase from nadir ² in the SPD of all index lesions

¹ At each assessment (if the index nodal lesions are not in CR status), the response status based on SPD calculation will be first assessed for meeting PD status criteria, then PR status and SD status.

² Nadir is defined as the smallest sum of the product of the diameters of all index lesions recorded so far, at or after Screening.

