14.2.4.1.3 Evaluation of response for all index lesions

The evaluation of response for all index lesions is based on the combination of the response for index nodal lesions (CR or non-CR), the response for index extranodal and the status based on the SPD calculated on all index lesions (nodal and extranodal), as described in [Table 14-9](#).

Table 14-9 Radiological response for index lesions

Response for index nodal lesions ¹	Response for index extranodal lesions ¹	Status based on SPD calculation for all index lesions	Response for index lesions
CR	CR	Not calculated	CR
CR	SD/ PR	Not calculated	PR
CR	PD	PD	PD
CR	PD	PR	PR
CR	PD	SD	SD
Non-CR	Not evaluated	PD	PD
Non-CR	Not evaluated	PR	PR
Non-CR	Not evaluated	SD	SD

¹ If no index nodal lesions are present at Screening, then index lesions response is equal to the index extranodal lesions response. A similar rule applied if no index extranodal lesions are present at Screening, then index lesions response is equal to the index nodal lesions response.

In case of missing measurements of any of the index lesions, the radiological response for index lesions at that assessment will be “Unknown (UNK)”, unless progression was seen.

All lesions must have been measured with the same method as the one used at Screening, otherwise the radiological response for index lesions at that assessment will be “Unknown (UNK)”.

14.2.4.1.4 Evaluation of non-index lesions (including nodal, splenic and/or hepatic nodules and other extranodal lesions)

At each reassessment, a non-index lesion (or a group of non-index lesions) will be given one of the following designations:

- Normalization (non-index nodal lesion has regressed to normal size; non-index extranodal lesion is no longer present). Normalization of non-index nodal lesions should be determined based on their size at Screening.
- Improved, stable or worsened, but without unequivocal evidence of disease progression (non-index lesion is present but there is not sufficient worsening to declare PD based on the existing non-index lesions).
- Unequivocal evidence of disease progression (worsening of existing non-index lesions is sufficient to declare PD).
- Not assessed.

Then, this status for each non-index lesion (or group of non-index lesions) will lead to a global response for non-index lesions ([Table 14-10](#)):

Table 14-10 Response criteria for non-index lesions (nodal, splenic and/or hepatic nodules and other extranodal lesions)

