6.2 Overall Response Rate (ORR)

Overall response is determined by investigator assessment for each tumor assessment in the study. For subjects with solid tumors (other than lymphoma) the assessment criteria will be RECIST 1.1 and will include responses of CR and/or PR; for lymphoma, Cheson criteria will be used; for hematologic tumors, other appropriate hematological response criteria will apply. The number and percentage of subjects for different categories of overall response (e.g., for solid tumors – CR, PR, SD, PD, Not Evaluable) will be provided for solid tumors (non-lymphoma), lymphoma (if applicable), and each hematological tumor type (if applicable). Ninety-five percent (95%) exact confidence intervals (CIs) will be provided for the response rate(s) (e.g., for solid tumors – CR and/or PR) as well. For cohorts with at least 10 subjects,

overall responses will be summarized separately. Components of tumor assessments (e.g., for solid tumors – target lesion response, non-target lesion response, new lesion [yes/no]) will also be listed. In addition, Cancer Antigen-125 (CA-125) (if applicable) in the assessment of ovarian cancer response, Prostate-specific Antigen (PSA) (if applicable) in the assessment of prostate cancer will be listed.

The above analyses will be performed for the FAS.

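### Appendix B gives two progression rules for existing lymphoma lesions that can disagree on the same scans, and no sentence says which governs

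*Protocol*

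**What the plan says.** Protocol 14.2.4 opens with "Definitions of Response for Lymphoma patients are listed in" Table 14-6. The relapse/PD row of that table has three triggers on existing lesions:

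- a rise of at least 50% in one node: "increase in longest diameter of a previously identified node > 1 cm in short axis";
- a rise of at least 50% in the SPD of more than one node;
- in the spleen/liver column, "> 50% increase from nadir in the SPD of any previous lesions".

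The same section then says that response at each assessment is evaluated through Table 14-9 (index lesions) and a non-index table, and combined in Table 14-11. In that chain, PD on index lesions depends on sums. Table 14-7 gives PD for "At least a 50% increase from nadir" in the SPD of all index lesions, and PR for "At least 50% decrease from Screening in the SPD of all index lesions". Table 14-8 applies the same thresholds to index extranodal lesions when the index nodes are in CR. Table 14-9 then combines the nodal response, "the response for index extranodal and the status based on the SPD calculated on all index lesions". Two of its rows take nodal CR with extranodal PD to PR or to SD, according to the all-index SPD status.

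SAP 6.2 says only that "for lymphoma, Cheson criteria will be used". Response is by local investigator assessment (protocol 7.2.1 and 10.4; SAP 6.1 and 6.2).

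**The concern.** Table 14-6 looks at single lesions and the later tables look at totals. When most disease shrinks and one site grows, the two can part company, and the appendix gives no order of precedence. Because sites make the call, two investigators could classify identical scans differently and both be following the protocol.

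The call feeds ORR, DOR and PFS, and in some cases the primary CBR. It also marks the point at which study treatment ends (protocol 4.1.1). B-cell lymphoma and ALCL are two of the six groups named in SAP 10.1, each with an expected accrual of 6 (SAP Table 1), so single patients weigh heavily.

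**Working it through.** The plan states no figure to reproduce. The check is to apply both rules to the same measurements. The lesion sizes are illustrative assumptions in mm; SPD is in mm².

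**Case 1, regrowth after nadir.** Three nodes. Baseline SPD 600 + 1200 + 2000 = 3800. Nadir 192 + 300 + 500 = 992. One node then goes from 16×12 to 26×18 (192 to 468), so the total is 468 + 300 + 500 = 1268.

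**Case 2, first assessment.** Screening 40×40, 40×40, 20×15: 1600 + 1600 + 300 = 3500. First assessment 20×20, 20×20, 30×18: 400 + 400 + 540 = 1340. Nadir so far is the Screening value.

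**Case 3, a Table 14-9 row.** Four index nodes normalised at 15×14 (210 each) and one liver lesion going from 10×10 to 20×20. Baseline 4×1200 + 500 = 5300. Nadir 4×210 + 100 = 940. Later 4×210 + 400 = 1240.

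| Case | Growing lesion | Total SPD vs nadir | Total SPD vs baseline | Table 14-6 | Tables 14-7/14-9 |
|---|---|---|---|---|---|
| 1 | longest diameter 26/16 − 1 = +62.5% | 1268/992 − 1 = +27.8% | 1268/3800 − 1 = −66.6% | PD | PR |
| 2 | longest diameter 30/20 − 1 = +50% | 1340/3500 − 1 = −61.7% | −61.7% | PD | PR |
| 3 | liver SPD 400/100 − 1 = +300% | 1240/940 − 1 = +31.9% | 1240/5300 − 1 = −76.6% | PD | PR (nodal CR, extranodal PD, all-index PR) |

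The PR carries through Table 14-11 if non-index lesions are CR or SD and there is no new lesion. The split can also run the other way. A single node going from 24×20 to 30×25 has SPD 750/480 − 1 = +56.3%, which is PD by Table 14-7. Its longest diameter rises 30/24 − 1 = +25%, and only one node is involved, so the nodal column of Table 14-6 is not met.

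**Does another provision settle it?** The 50% long-axis rule under new lesions (14.2.4.2) applies to an abnormal lymph node, which 14.2.2.2 defines as not disease related and not a lesion, so it does not reach an index node. The Table 14-7 footnote puts PD first, but only by that table's own SPD rule. Section 14.2.4.2.4 passes any non-CR radiological result unchanged to overall response.

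**When CBR is affected.** Under SAP 6.1, progression before week 16 means no clinical benefit. So does progression at or after week 16 with no CR, PR or SD at or after week 16. With scans every 8 weeks, a disputed PD at week 8 or at the week-16 scan matters. One first seen at week 24, after PR or SD at week 16, does not.

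**Weight of one patient.** 1/6 = 16.7 points. To show scale, take Pr(π_g > R_g) for n = 6 from a single-group prior without borrowing: θ ~ N(0, v + 0.25). Here 0.25 = 0.5/(3 − 1) is the mean of IG(3, 0.5), and v is 1.82 or 1.82² = 3.31, because the plan does not say whether 1.82 is a variance or an SD. R is from SAP Table 1.

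| Group (R) | 5/6 | 6/6 |
|---|---|---|
| B-cell lymphoma (0.60) | 0.867 to 0.886 | 0.974 to 0.984 |
| ALCL (0.90) | 0.396 | 0.772 to 0.815 |

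**The case against.** The strongest reply is that the working procedure can be identified. Section 14.2.4 names the tables to be used at each assessment, 14.2.4.2.1 says overall radiological response is calculated from Table 14-11, and 14.2.4.2.4 carries the result forward. Protocol 7.2.1.2 calls the criteria modified. On that reading Table 14-6 is background and Tables 14-7 to 14-11 are the algorithm. This is the more natural reading. But Table 14-6 is introduced as the definitions, nothing makes it subordinate, and it gives different answers.

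A reader might infer that the Table 14-9 rows are simply errors. The documents do not support that: 14.2.4.1.2 explains why extranodal lesions are assessed separately once nodes normalise, and the rows look deliberate. The point is only that they disagree with Table 14-6.

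A reader might also infer that lymphoma scans will generally be scored in opposite ways. Disagreement needs particular lesion patterns, chiefly one site growing while the total falls, and the documents give no basis for a frequency. The effect on PFS is also diluted, because SAP 6.3 reserves separate PFS analyses for cohorts of at least 10.

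**Conclusion.** Two stated rules conflict, and ordinary mixed-response measurements are enough to turn PD into PR. ORR, DOR and PFS can change for the lymphoma patients concerned; CBR can change only under the timing condition above. The weight is about 17 points of CBR per patient in a cohort of 6.

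It would be tempting to say that one patient decides a cohort's verdict. That holds only narrowly. For B-cell lymphoma without borrowing, 5/6 and 6/6 fall on either side of the 0.90 threshold in the SAP and protocol 10.4.3. Both exceed the 0.80 in Appendix Q, taking the same R. ALCL reaches 0.90 in neither case; at 0.80, its 6/6 result depends on how the prior is read. The planned model borrows across groups, so these posteriors show scale, not the result the trial would report.

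Nothing here says which progression rule is right. The passages must be reconciled.

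**What to change.** - **Protocol 14.2.4:** state which table governs progression on existing lesions and make the other agree, including the two Table 14-9 rows if they are affected.
- **Cross-reference:** 14.2.4 sends non-index lesions to Table 14-8, which is the index extranodal table. It should point to Table 14-10, as 14.2.4.1.4 already does.
- **SAP 6.1 to 6.3:** keep the investigator assessment under the governing table as primary. As a sensitivity analysis, report lymphoma CBR, ORR and PFS re-derived from the recorded lesion diameters under the other table. SAP section 2 records early termination, so this is the part that can still bear on the analysis.

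Counting PD under either table as PD would not be a good substitute. It is stricter than both tables and would displace the investigator assessment that protocol 7.2.1 fixes for analysis and treatment decisions.

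The cost is some wording and a little programming, since index lesion sizes are entered on the eCRF (14.2.3.1.2). Lymphoma CBR or ORR may be slightly lower in one of the two analyses. One limit should be stated with the results: disease assessments stop at progression or end of treatment (4.1.1), so a patient taken off at a PD that the other table would not call has no later scans to re-derive.
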